3.7.3 Safety Monitoring For Kidney toxicity: Management and Stopping Rules

If subjects develop a creatinine elevation > 2xULN and more than 2x Baseline value:

- Monitor creatinine 2 times per week, or as clinically indicated, until recovery.
- For subjects with > 3xULN creatinine elevation the study drug should be withheld and the subject should continue to be followed closely.
- In the event of either of the above continued participation in the study should be discussed with the Medical Monitor.

Discontinuation:

Discontinuation of study drug should be considered, in consultation with the Medical Monitor and Reneo CMO or designee where possible, if:

- A > 3xULN creatinine elevation is sustained or deteriorating.
- The subject is unwell and has hyperkalemia.

3.8 Replacement of Subjects

Subjects who withdraw due to reasons other than AEs or SAEs may be replaced to ensure that sufficient subjects are available to satisfy the statistical assumptions of the study.

3.9 Temporary Discontinuations

Subjects may be temporarily discontinued from study drug while AEs and/or laboratory test abnormalities are being investigated and/or at the request of the Medical Monitor. The Investigator should discuss with the Medical Monitor and Sponsor any subject for whom temporary or permanent discontinuation of study drug is being considered.

If a subject misses several consecutive doses due to personal circumstances or due to an AE not related to study drug, they may be allowed to restart dosing after discussion between the Investigator, Medical Monitor and Sponsor (See [Section 5.9](#)).

3.10 Review of Screening Eligibility Data

An independent Patient Screening Oversight Committee with experts in the diagnosis of PMM will be set up to review screening data to ensure subjects enrolled into the study have the correct diagnosis of PMM. Details regarding the structure, function and operation of the PSOC will be detailed in the REN001-201 PSOC Charter.

3.11 Review of Safety Data

Review of subject safety data (including, but not limited to, AEs, ECGs, laboratory safety tests and vital signs) will be performed by the independently chaired Safety Review

Committee (SRC) in accordance with the REN001-201 SRC Charter. Safety reviews will be conducted throughout the study in order to identify any potential safety signals during the trial that may have an impact on the safety of the participants. The SRC may make recommendations concerning continuation, termination or study modifications based on these reviews.

4 STUDY POPULATION

To fulfil the study objectives, it is essential that appropriate subjects are enrolled. The following eligibility criteria are designed to select subjects considered appropriate for participation in the study. Subject eligibility should be reviewed and documented by the Investigator or an appropriate designee member of the site study team. In addition, subjects screening data will be reviewed independently by the PSOC for confirmation of eligibility prior to randomization.

4.1 Inclusion Criteria

Subjects must meet all of the following inclusion criteria to be eligible for inclusion in the study:

1. Subjects aged 18 years or older with PMM as defined by the International Workshop: Outcome measures and clinical trial readiness in primary mitochondrial myopathies in children and adults ([Mancuso et al 2017](#)) (see [Appendix 1](#)).
2. A confirmed PMM diagnosis due to a known pathogenic gene mutation or deletion of the mitochondrial genome. The Sponsor may authorize local genetic testing at Screening, if required, but results must be available prior to randomization of the subject (see [Sections 6.1](#) and [7.1.24](#) for details).
3. Documented PMM primarily characterized by exercise intolerance or active muscle pain.
4. Subjects must be ambulatory and able to perform the 12MWT independently (walking aids are allowed).
5. Distance walked of ≤ 1000 meters at Screening in the 12MWT (must be obtained at least 4 weeks before randomization).
6. Have no changes to any therapeutic exercise regimen within 30 days prior to Day 1 and be willing to remain on the same therapeutic exercise regimen for the duration of the study.
7. Be willing and able to swallow gelatin capsules.
8. Females should be either of non-child-bearing potential or must agree to use highly effective methods of contraception from Screening through to 30 days after last dose in the study. Where females are using hormonal contraception therapy, an additional effective non-hormonal method of contraception is advised. Males with partners who are WOCBP must also use contraception (See [Section 5.10](#) for details).
9. Concomitant medications (including supplements) intended for treatment of PMM or other co-morbidities must be stable for at least 1 month prior to randomization and throughout participation in the study.
10. For subjects under 25 years old only: confirmation of bone growth plate closure by wrist radiograph.
11. Evidence of a personally signed and dated informed consent document indicating that the subject has been informed of all pertinent aspects of the study.

4.2 Exclusion Criteria

Subjects presenting with any of the following will not be included in the study:

1. Participation in a prior REN001 (previously known as HPP-593) study.
2. Currently taking or anticipated to need a PPAR agonist during the study.

3. Bone deformities or motor abnormalities other than related to the mitochondrial myopathy that may interfere with the outcome measures.
4. Treatment with an investigational drug within 3 months or 5 drug half-lives, whichever is longer, prior to Day 1.
5. Anticipated to need a prescription and/or non-prescription drug that might interfere with the study endpoints (See [Table 1](#)).
6. Currently taking drugs with a narrow therapeutic index and BCRP mediated ADME e.g., aliskiren, ambrisentan, colchicine, digoxin, everolimus, imatinib, lapatinib, maraviroc, nilotinib, posaconazole, ranolazine, saxagliptin, sirolimus, sitagliptin, talinolol, tolvaptan, topotecan, methotrexate, mitoxantrone, irinotecan, rosuvastatin, and sulfasalazine (See [Table 1](#)).
7. Clinically significant kidney disease or impairment, with an eGFR less than 60ml/min/1.73m² using the CKD-EPI creatinine equation at Screening.
8. Clinically significant liver disease or impairment, with AST or ALT >2.5 x ULN, or Total bilirubin > 1.6 x ULN or >ULN with other signs and symptoms of hepatotoxicity at Screening. *(Subjects with an isolated elevated bilirubin (e.g., < 2 x ULN) may be included after discussion with the Medical Monitor if the cause is due to a benign hereditary disorder of metabolism such as Gilbert's syndrome.)*
9. Uncontrolled diabetes and/or a Screening HbA1c of ≥11%.
10. Uncontrolled epilepsy.
11. Evidence of significant concomitant clinical disease that may need a change in management during the study or could interfere with the conduct or safety of this study. *(Stable well-controlled chronic conditions such hypercholesterolemia, gastroesophageal reflux, or depression under control with medication (other than tricyclic antidepressants), are acceptable provided the symptoms and medications would not be predicted to compromise safety or interfere with the tests and interpretations of this study.)*
12. A history of cancer. A history of *in situ* basal cell carcinoma in the skin is allowed.
13. Have been hospitalized within the 3 months prior to Screening for any major medical condition (as deemed by the Investigator).
14. Clinically significant cardiac disease and/or clinically significant ECG abnormalities including a screening QTcF of ≥ 450 msec, 2nd degree heart block, symptomatic tachyarrhythmia or unstable arrhythmia that in the opinion of the Investigator should exclude the subject from completing the study exercise tests (i.e., 12MWT and 30STS tests). *(Subjects with right bundle branch block, left fascicular block and long PR interval which are common in PMM may be enrolled if the Investigator considers that the condition would not compromise safety or interfere with the tests and interpretations of this study.)*
15. Any condition possibly reducing drug absorption (e.g., gastrectomy or increased motility).
16. Evidence of hospitalization for rhabdomyolysis within the year prior to enrolment.
17. Positive HBsAg and HBcAb at Screening, or positive for hepatitis C or HIV at Screening.
18. Pregnant or nursing females.
19. History of sensitivity to PPAR agonists.

20. Donation or intent to donate blood, or blood components during the study or within one month after completion of the study.
21. A history of drug dependency. Use of opiates/cannabis for medical reasons is acceptable with prescription evidence or at the Investigators discretion.
22. A history of alcohol dependency.
23. Significant impairment due to central or peripheral nervous system involvement that would interfere with the exercise tests.
24. Significant weakness not caused by the underlying primary muscle disease such as post stroke or neurogenic weakness.
25. Have had an organ transplant.
26. Are not eligible or have a contraindication for cataract surgery.
27. A history of osteoporosis as evidenced by non-traumatic (stress) fractures or a prior T-score of -2.5 or worse which has not been adequately addressed.
28. Inability to comprehend or unwilling to follow the study requirements including restrictions on treatments, attendance at the study center, completion of questionnaires and participation in laboratory testing as called for by the protocol.
29. Any other severe acute or chronic medical or psychiatric condition or laboratory abnormality that may increase the risk associated with study participation or investigational product administration or may interfere with the interpretation of study results and, in the judgment of the Investigator, and in discussion with the Medical Monitor, would make the subject inappropriate for entry into this study.

4.3 Planned Sample Size and Number of Study Centers

It is envisaged that approximately 265 subjects will be screened to achieve 200 randomized subjects. Recruitment will be from across a minimum of 35 centers worldwide.

5 STUDY DRUG

5.1 Study Drug Identity

Study drug and placebo are presented as Swedish orange, hard gelatin, size 0 capsules, manufactured by Xcelience LLC, a Lonza company.

The dosage strength of REN001 capsules is 50 mg. Matched placebo capsules will also be supplied, containing approximately 30 mg microcrystalline cellulose.

Capsules are packaged in 200 mL high-density polyethylene (HDPE) bottles, with a heat induction seal and child-resistant lids, containing 100 capsules of either 50mg REN001, or placebo. Supplies will be identified by the blinded batch number and expiry date.

As each subject will take 2 capsules per day the bottle will contain sufficient capsules for 50 days of dosing.

Sufficient bottles will be supplied to ensure subjects have at least enough capsules to maintain dosing between Study Center visits.

5.2 Allocation to Treatment

Upon Screening, each subject will receive a 6 digit study number allocated by the Integrated Web-based Response System (IWRS), which will be used throughout the study. The IWRS will use a computer-generated randomization schedule to assign subjects to a treatment sequence on a 1:1 basis. The randomization will be stratified by both mutational genotype (m.3243A>G or other mitochondrial DNA defects) and the screening 12-minute walk distance (12MWD) (≤ 500 meters or > 500 meters).

Screened subjects who drop out of the study before receiving study drug or require repeat safety lab tests will retain their study number. A subject may be rescreened once only (with prior approval by the Sponsor); for instance, if a washout of prior medications of longer than 6-8 weeks is required. Rescreened subjects will be given a new study number and their previous study number will also be recorded.

5.3 Maintaining the Blind

This study is a double-blind study i.e., the study will be Sponsor, subject- and investigator-blinded. All personnel involved in the conduct of the study will remain blinded to treatment until the conclusion of the study. To minimize the potential for bias, treatment randomization information will be kept confidential by the IWRS vendor and will not be released to the Sponsor, Investigator, site personnel, or the study monitors until the conclusion of the study.

REN001 and placebo will be provided as visually matched capsules. All study drug will be supplied in identical bottles thereby maintaining the double blind conditions for the subject and Investigator.

5.4 Breaking the Blind

Details of personnel who will be unblinded to subject data during the study will be recorded in a document maintained by the Sponsor.

At the initiation of the study, the study site will be instructed on the method for breaking the blind. The study blind should not be broken except in a medical emergency, where knowledge of the study drug received would affect the treatment of the emergency or obtaining this information is a regulatory requirement. As a courtesy, and only if time permits, the Investigator may notify the Sponsor prior to unblinding. All Investigator unblinding events will be automatically reported by the IWRS to the Sponsor.

If the blind is broken, the date, time and reason must be recorded in the subject's eCRF. Information concerning the treatment allocated should only be available to those who need to know for the appropriate action to be taken with the subject.

5.5 Administration

Subjects will receive either 100 mg REN001 as 2 x 50 mg or placebo as 2 x placebo capsules for oral administration once daily for 24 weeks.

Medication should be taken with food, for consistency of exposure, at a convenient time to the subject (ideally in the morning). The exception to this will be when the subject is required to attend the Study Center for their Baseline, Week 12 and Week 24 Visits, when they should take the study medication at the Study Center, when instructed to do so, by the site staff. On these visits, sites will ensure the subjects take the study medication with food.

Subjects will be supplied with a dose recording card and will be requested to record the date and time of dosing for study visit days (other than Baseline, Week 12 and Week 24).

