Subjects will either attend the Study Center or receive a home nursing visit (in countries where the regulatory authority allows) on Day 14. On this day, the subject will take their daily dose at home as usual and record the time of dose on the subject dosing card. The following assessments will be carried out:

- Review concomitant medications, non-drug treatments and study medication compliance
- Review of adverse events
- Vital signs (including temperature)
- Obtain blood samples for:
 - Hematology
 - Biochemistry
 - Plasma sample for pharmacokinetic analysis of REN001
- Obtain urine samples for:
 - Urinalysis
- Capsule counts of remaining capsules including any opened IMP bottles

Subjects will be reminded of the study restrictions and instructed on study medication dosing requirements.

6.4 Weeks 4 and 18 (Days 28 and 126): Visits 4 and 6

Subjects will either attend the Study Center or receive a home nursing visit (in countries where the regulatory authority allows) on Days 28 and 126. On these days, the subject will take their daily dose at home as usual and record the time of dose in the subject dosing card. The following assessments will be carried out:

- Review concomitant medications, non-drug treatments and study medication compliance
- Review of adverse events
- Vital signs (including temperature)
- Obtain blood samples for:
 - Hematology
 - Biochemistry
 - Plasma sample for pharmacokinetic analysis of REN001
- Obtain urine samples for:
 - Urinalysis
 - Urine for pregnancy testing (WOCBP Week 4 only)
- Review of last 7 days pedometer data
- MFIS
- BPI
- SF-36
- PGIS – muscle symptoms
- PGIS – fatigue symptoms
- PROMIS Short Form – FACIT Fatigue 13a

- WPAI:SHP
- Capsule counts of remaining capsules including any opened IMP bottles

Subjects will be reminded of the study restrictions and instructed on study medication dosing requirements.

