6.5 Weeks 8, 16 and 20 (Days 56, 112 and 140)

Subjects who are WOCBP at risk of pregnancy will be supplied with urine pregnancy tests to use at home at Weeks 8, 16 and 20. Study Center staff will need to contact the subjects by telephone to obtain the result of the pregnancy test and enter the result into the eCRF. Subjects may be given a reminder telephone call to conduct the test if necessary.

6.6 Weeks 12 and 24 (Days 84 and 168): Visits 5 and 7

Site staff will need to provide subjects with meals and snacks at appropriate times during the visit to ensure subjects have enough energy prior to completing the exercise tests.

Subjects will attend the Study Center on Days 84 and 168. On these days, the subject will take their daily dose in the Study Center. The following assessments will be carried out:

- Obtain second morning void urine sample for:
 - Bone marker - NTX
 - Urinalysis
 - Drugs of abuse
 - Urine for pregnancy testing (WOCBP only)
- Obtain blood samples for:
 - Hematology (including HbA1c at Week 24 only)
 - Biochemistry
 - Additional bone and calcium metabolism markers
 - Pre-dose plasma sample for pharmacokinetic analysis of REN001
- Administer the study drug with food under supervision of clinical staff and the time of dosing recorded.
- Review concomitant medications, non-drug treatments and study medication compliance
- Review of adverse events
- Physician completion of subjects PMM phenotypic description (Week 24 only)
- Review of pedometer eDiary data
- Brief physical examination (including weight)
- 12-lead ECG
- Vital signs (including temperature)
- Obtain plasma samples for pharmacokinetic analysis of REN001 (1, 2, 3 and 4* hours postdose)
- Review of last 7 days pedometer data
- MFIS
- BPI
- SF-36
- PGIS – muscle symptoms

- PGIS – fatigue symptoms
- PGIC – muscle symptoms (Week 24 only)
- PGIC – fatigue symptoms (Week 24 only)
- PROMIS Short Form – FACIT Fatigue 13a
- WPAI:SHP
- 12MWT
- 30STS
- Capsule counts of remaining capsules including any opened IMP bottles
- Subjects will be provided with a urine collection cup and instructions for collecting a second morning void at the Week 24 visit if they are unable to do this at the Study Center for any reason (Week 12 only)
- Eye examinations (may be completed \pm 14 days of the visit if required)

Assessments should be conducted to ensure that the PRO questionnaires are completed prior to exercise testing and the 12MWT must be done at least 1 hour before the 30STS.

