14. At the Baseline, Week 12 and Week 24 visits, blood samples will be taken pre-dose and then at 1, 2, 3, and 4 hours post-dose. On the other visits, a single sample can be taken at any time post-dose provided the dosing date and time are recorded.
15. Review of Screening (pre-treatment) pedometer data at Baseline.
16. Screening 12MWT must be at least 4 weeks before the Baseline 12MWT.
17. The Screening eye examination can be performed at any time between the initial Screening and Baseline Visit for scheduling reasons.
18. Subjects <25 years old only.
19. Dosing on Baseline, Week 12 and Week 24 visits should be under the supervision of the site staff.

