8.7 Pharmacokinetic Endpoints

Plasma concentrations of REN001 will be summarized over time using descriptive statistics for Day 1, Week 12 and Week 24.

Individual subject concentration-time data on Day 1, Week 12 and Week 24 will be plotted over actual PK sampling times. Median profiles of the concentration-time data, using nominal PK sampling times, will also be presented for Day 1, Week 12 and Week 24. Both linear-linear and linear-log plots will be presented.

The data will be used for a population PK analysis which will be reported as a standalone report to the Clinical Study Report.

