11. ANALYSIS OF PHARMACOKINETIC ENDPOINTS

The mavodelpar concentrations will be evaluated using the PK set. mavodelpar concentrations will be summarized at each scheduled time point on Day 1 and Weeks 12 and 24 using descriptive statistics. For post-dose samples, only concentrations collected within a 10% window of the protocol specified post dose time point will be included. Similarly, pre-dose concentrations will only be included if the samples were taken prior to dosing on the day. The number of subjects with a BLQ value will also be tabulated.

Linear and log-linear individual concentration profile spaghetti plots against time will be produced for Day 1 and Weeks 12 and 24. All subjects will be displayed on the same plot and mutational genotype (m.3243A>G, m.8344A>G, mt deletion or Other) will be identified. The actual sampling time will be used on the x-axis with pre-dose fixed at zero for all subjects.

Linear and log-linear median concentration profile plots against time will be produced for Day 1 and Weeks 12 and 24. The nominal sampling time will be used on the x-axis. Lines will be included for all subjects and by mutational genotype.

A listing of all concentration data will be presented. The actual time post dose, deviation and percent deviation from nominal post dose time will also be listed for the post dose samples on Day 1 and Weeks 12 and 24. For all other visits the actual time relative to dose the sample was collected will be listed.

Concentration values will be presented to 3 significant figures.

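### Neither document requires the time of the dose before the Week 12 and Week 24 pre-dose PK samples, and SAP 11 pools these concentrations with no check on time since dose

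*Protocol*

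**What the plan says.** Protocol 5.5 lets subjects take the daily dose "at a convenient time to the subject (ideally in the morning", so evening dosing is allowed though not preferred. The dose card is limited: subjects are "requested to record the date and time of dosing for study visit days (other than Baseline, Week 12 and Week 24".

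For Weeks 12 and 24, Protocol 6.6 lists "Pre-dose plasma sample for pharmacokinetic analysis of REN001" and then instructs staff: "Administer the study drug with food under supervision of clinical staff and the time of dosing recorded". Serial samples follow up to 4 hours after that dose.

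For Week 2, Protocol 6.3 says "the subject will take their daily dose at home as usual and record the time of dose on the subject dosing card"; Protocol 6.4 is almost the same for Weeks 4 and 18. For visits other than Baseline, Week 12 and Week 24, footnote 14 of Table 2 says that "a single sample can be taken at any time post-dose provided the dosing date and time are recorded". The Early Termination list in Protocol 6.8 includes a PK sample but no dosing-time item.

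SAP 11 applies a 10% window to post-dose samples. For the others its only test is that "pre-dose concentrations will only be included if the samples were taken prior to dosing on the day". It lists actual time after dose for the post-dose samples on Day 1 and at Weeks 12 and 24, and time relative to dose for all other visits. In the individual plots every pre-dose sample is placed at time zero. Protocol 8.7 adds: "The data will be used for a population PK analysis".

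**The concern.** A Week 12 or Week 24 pre-dose concentration comes from the preceding doses, chiefly the last one. The dose time that staff record belongs to a dose given after the sample, so it says nothing about how long the drug had been declining. Followed as written, the plan leaves these concentrations without a known time after dose.

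Two outputs depend on that time. The pre-dose summary and the median profile at Weeks 12 and 24 may combine values from different points of the dosing interval. The population PK analysis needs a dose history for each sample. The other samples at these two visits end at 4 hours, so the pre-dose samples carry useful information on the later part of the curve. Plasma concentration is the only PK endpoint, and it is hard to interpret without time since dose.

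**Working it through.** **1. Which dose time the text collects, sample by sample**

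| Sample | Dose behind the concentration | Dose time requested | Time since dose listed in SAP 11 |
|---|---|---|---|
| Baseline pre-dose | none | not needed | not needed |
| Baseline, Weeks 12 and 24, 1–4 h | clinic dose | yes, by staff | yes, with 10% window |
| **Weeks 12 and 24 pre-dose** | **preceding dose, normally at home the day before** | **none** | **no** |
| Weeks 2, 4, 18, morning doser | that morning's dose | yes, on the card | yes |
| Weeks 2, 4, 18, evening doser sampled before that day's dose | previous evening's dose | footnote 14 requires a recorded dose; card and visit text ask for the visit-day dose, which comes later | yes |
| Early Termination | last dose before stopping | footnote 14 requires it; neither the card instruction nor Protocol 6.8 asks for its clock time | yes |

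The Week 12 and 24 pre-dose samples are the only on-treatment samples for which neither the collection rule nor the listing rule supplies a time since dose. Capsule counts (Protocol 5.9) carry no times, and the eDiary (7.1.21) is described only for step counts.

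**2. Number of samples.** Three visits × 5 samples + Weeks 2, 4 and 18 = 18, which reproduces the count in Protocol Table 4. Two of 18 (11%) have no prescribed dose time in any subject. In an evening doser seen by day, the card misses the relevant dose for up to 3 more (5 of 18, 28%), but footnote 14 does require a dose time for those three. An Early Termination sample would be additional.

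**3. Possible spread in time after dose.** Hours since dose = sample time + 24 − previous-day dose time. All clock times are assumptions.
- Dose 19:00, sample 09:00: 9 + 24 − 19 = 14 h.
- Dose 09:00, sample 09:00: 9 + 24 − 9 = 24 h.
- Samples at 08:00–11:00: 10–17 h after an evening dose (18:00–22:00), and 22–28 h after a morning dose (07:00–10:00).

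**4. Effect on the level.** With first-order decline, the ratio of a 14 h to a 24 h level is 2^(10/t½). No half-life is given in the documents, so t½ is assumed. If a quarter of subjects dosed in the evening (also assumed), the mean pre-dose level relative to all-morning dosing is 0.75 + 0.25 × ratio.

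| Assumed t½ | Ratio 14 h : 24 h | Mean with 25% evening dosers |
|---|---|---|
| 6 h | 3.17 | 1.54 |
| 12 h | 1.78 | 1.20 |
| 24 h | 1.33 | 1.08 |
| 48 h | 1.16 | 1.04 |

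**5. Contrast within SAP 11.** Ten percent of 60 minutes is 6 minutes, so a 1-hour sample that is 7 minutes off is dropped. The same 10% around 24 h would be 21.6–26.4 h. The whole assumed evening range lies outside it, yet all those samples enter the pre-dose summary.

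**The case against.** The strongest reply is that the documents show less than a reader might infer.

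- **That the dose time is never recorded.** This cannot be concluded. The eCRF, the Laboratory Manual and the separate population PK plan named in SAP 5 are not among the documents, and any of them might capture it. What can be said is that the protocol and SAP do not require it.
- **That Weeks 2, 4, 18 and Early Termination share the gap.** They do not. Footnote 14 makes those samples conditional on a recorded dosing date and time, and SAP 11 lists their time relative to dose. Morning dosers at Weeks 2, 4 and 18 are fully covered. What remains is that the collection instructions do not always deliver what footnote 14 demands. At Early Termination the SAP already relies on the date of last dose (8.2 and 9.5), so at most the clock time is missing, and that matters less when the visit falls days or weeks after the last dose.
- **That the population PK estimates will be biased.** The analysis plan is not available. A model could leave these samples out or allow for uncertain dose times. Weeks 2, 4 and 18 also provide up to three samples at any time after dose, so the pre-dose samples need not be the only late data.
- **That the effect is large.** Half-life, clock times and the share of evening dosers are all assumed, and the protocol prefers morning dosing. With a long half-life or few evening dosers, little changes.

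All of this stands, and it limits the point. None of it supplies a required dose time for the Week 12 and 24 pre-dose samples, or a rule in SAP 11 for telling a 14 h value from a 24 h value.

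**Conclusion.** The concern holds in limited form. The protocol and SAP do not require the date and time of the dose preceding the Week 12 and Week 24 pre-dose samples, and SAP 11 pools those concentrations without a window or a listing of time since dose. For one pair of samples the distortion could be about 3-fold or about 16%, depending on a half-life the documents do not give; for the group mean it also depends on how many subjects dose in the evening. As a separate and smaller matter, Protocol 5.5, 6.3, 6.4 and 6.8 do not fully match footnote 14 and should be reconciled with it.

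The consequence is confined to the PK summaries, plots and population PK analysis in subjects who receive REN001, since the PK set excludes placebo (Protocol 8.1.3, SAP 7.7). Efficacy and safety conclusions are not affected. It is a cheap improvement, not a threat to the trial's main result.

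**What to change.** - **Protocol 5.5 and Table 2 footnote 14:** have the card and eCRF record the date and time of the last dose taken before every PK sample. This covers the dose before the Week 12 and 24 visits, the preceding dose at Weeks 2, 4 and 18 when that day's dose has not yet been taken, and the last dose before Early Termination. Bring 6.3, 6.4, 6.6 and 6.8 into line. Only recording changes, not dosing.
- **SAP 11:** list time since last dose for the Week 12 and 24 pre-dose samples, and state that the population PK analysis will use actual times. Apply a prespecified time-since-dose window, chosen by the sponsor, to the pre-dose summary. Extending the SAP's own 10% rule to 24 h, for example, gives 21.6–26.4 h. Values outside the window, or with unknown time, would be listed but not summarised.

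The cost is a small protocol amendment, one more entry on an existing card and eCRF page at every center, and a few sentences in the SAP. Some values would leave the pre-dose summary. Under a 21.6–26.4 h window these would include some morning dosers: a 07:00 dose and a 10:00 sample give 27 h. Dose times that were not collected cannot be recovered later, so for visits already completed only the SAP part can help.
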